4.11.5 Vital Signs

The following vital signs measurements will be assessed at screening, Visit 3 (Day 7), Visit 5 (Days 28) and Visit 9 (EOS):

- Systolic blood pressure (SBP) [mmHg].
- Diastolic blood pressure (DBP) [mmHg].
- Heart rate (bpm).
- Body temperature (oral) [°C].
- Respiratory rate (breaths/per minute)

Systolic blood pressure, diastolic blood pressure and heart rate will be classified as normal or abnormal

For by-visit summaries, the last non-missing assessment (including repeat assessments) recorded at each visit will be summarized. Baseline is defined as the last assessment prior to study drug intake and will be the screening assessment.

The following summaries will be based on the Safety Analysis Set and provided by study treatment group and assessment day:

- A summary of vital signs and change from baseline
- Vital signs: number and percentage of patients with normal or abnormal values

A listing of vital signs results will be provided.

4.11.6 Resting 12-lead Electrocardiograms

Single 12-lead ECG will be recorded at screening, Visit 3 (Day 7), Visit 5 (Days 28) and Visit 9 (EOS) and the following parameters will be obtained:

- Heart rate (bpm)
- PR interval
- QRS complex (msec)
- QT interval (msec)
- QTcF interval (msec)
- PR segment
- ST segment

The ECG will be evaluated by the Investigator as 'Normal', 'Abnormal, non-clinically significant (NCS)' or 'Abnormal, clinically significant (CS)'.

Baseline is defined as the last assessment prior to study drug intake and will be the screening assessment.

The following summaries will be based on the Safety Analysis Set and provided by study treatment group and assessment day:

- A summary of 12-lead ECG and change from baseline
- 12-lead ECG: number and percentage of patients with normal, abnormal NCS and abnormal CS values

A listing of 12-lead ECG results will be provided.

4.11.7 Physical examination

A complete physical examination will be performed at screening, Visit 5 (Days 28) and Visit 9 (EOS) and will include assessments of the head, eyes, ears, nose, throat, skin, thyroid, neurological, lungs, cardiovascular system, abdomen (including liver and spleen), lymph nodes, genitourinary system (optional) and extremities (musculoskeletal system).

The following summaries will be based on the Safety Analysis Set and provided by study treatment group and assessment day:

- Physical examination: number and percentage of patients with abnormal findings by physical site

A listing of physical examination will be provided.

4.11.8 Weight and BMI

Weight will be measured at screening, Visit 5 (Days 28) and Visit 9 (EOS).

Body mass index (BMI) will be calculated from the height in meter and weight in kg recorded and rounded off to the nearest whole number.

$$\text{BMI} = [\text{weight}/\text{height}^2] \text{ (kg/m}^2\text{)}.$$

Baseline is defined as the last assessment prior to study drug intake and will be the screening assessment. Absolute and relative change from baseline will be calculated as follows:

- Absolute change at Visit x= weight at Visit x – weight at baseline
- Relative change at Visit x= (weight at Visit x – weight at baseline) / weight at baseline

The following summaries will be based on the Safety Analysis Set and provided by study treatment group and assessment day:

- A summary of Weight with absolute and relative change from baseline
- A summary of BMI with absolute and relative change from baseline

Weight and BMI will be listed together with vital signs.

4.11.9 Safety Monitoring (Independent Data Monitoring Committee [IDMC], Data Monitoring Committee [DMC], Data and Safety Monitoring Board [DSMB])

Not applicable

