8.1.4 Weight and Height

Weight and height will be measured wearing light clothes and without shoes. Body mass index (BMI) will be calculated from the height and weight recorded and rounded off to the nearest whole number.

The body weight recorded at screening will be used for determination of eligibility and the body weight recorded at baseline, after the 4-week double-blind period and at the End of Study is a safety assessment. The method of weight assessment should be the same across all visits.

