8.3.2 Weight and BMI

Weight will be measured wearing light clothes and without shoes as designated on the SoA. The method of weight assessment will be the same across all visits. Body mass index (BMI) unit is kg/m^2 and calculated as weight in kg and height in meter.

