4.6 Demographics and Baseline Characteristics

The following summary and listing of demographic and baseline characteristics will be based on the FAS:

- A summary of demographic variables: age (years), sex, ethnicity, race, childbearing potential (female only), height (cm), weight (kg), BMI (kg/m^2) and LA grade by study treatment group and overall
- A summary of demographic variables by LA grade by study treatment group and overall
- A summary of viral serology results at baseline
- A summary of H.Pylori results at baseline
- Listing of demographics
- Listing of viral serology and H.Pylori at baseline

Age will be calculated as the number of complete years between a patient's birth date and the date of informed consent.

BMI is calculated automatically in eCRF as [weight/height²] (kg/m^2).

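### BMI is rounded to a whole number in its derivation, which coarsens the planned summary of BMI change; deleting the rounding is a free improvement

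*SAP*

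**What the plan says.** Two places carry the rounding rule. Protocol 8.1.4 says "Body mass index (BMI) will be calculated from the height and weight recorded and rounded off to the nearest whole number". SAP 4.11.8 repeats it for the safety analysis: BMI comes from the height and weight "recorded and rounded off to the nearest whole number".

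Two places define the same variable and do not mention rounding. Protocol 8.3.2 has BMI "calculated as weight in kg and height in meter". SAP 4.6 says "BMI is calculated automatically in eCRF as" weight over height squared.

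SAP 4.11.8 then plans two change summaries, "A summary of Weight with absolute and relative change from baseline" and "A summary of BMI with absolute and relative change from baseline". The only change formula is for weight ("weight at Visit x – weight at baseline", and the same difference divided by baseline weight). There is no BMI change formula, and nothing states whether rounding comes before or after the subtraction.

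BMI is a listed safety endpoint (Protocol section 3, SAP section 2). Protocol 9.4.8 has weight and BMI shown for each patient as well as summarised, with absolute and percent change. Height is measured only at screening (schedule of assessments, footnote 2). Inclusion criterion 3 sets limits of 18 and 40 kg/m², both inclusive, with no reference to rounding.

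**The concern.** A whole BMI unit is a large step compared with the weight change that four to eight weeks might produce. If both the baseline and the follow-up BMI are rounded first, each patient's change can only be a whole number. Small changes are then recorded either as nothing or as a full unit. The spread, the median, the quartiles, the range and the by-patient values would reflect the rounding grid as much as the patients.

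The BMI table would also disagree with the weight table in the same section. With height fixed at screening, relative BMI change should equal relative weight change exactly, and rounding breaks that identity.

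A secondary point arises in Protocol 8.1.4, where the rounding rule stands immediately before the statement that screening body weight is used for eligibility. The protocol does not say whether a rounded or an unrounded BMI is compared with the limits of criterion 3.

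**Working it through.** The plan gives no figure to reproduce here. The check is rounding arithmetic plus a simulation.

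**Inputs from the documents:** rounding step of 1 kg/m² (Protocol 8.1.4, SAP 4.11.8); 48 patients per arm (Protocol 6.3.1); limits of 18 and 40 kg/m² (criterion 3). **Assumed, because the documents do not give them:** height 1.70 m with a range of 1.55 to 1.90 m; mean weight change 0 to 3 kg with SD 1 or 2 kg; baseline BMI mean 28, SD 4, kept within 18 to 40.

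1. *Size of one BMI unit.* Kilograms per unit = height². This is 1.55² = 2.40 kg, 1.70² = 2.89 kg and 1.90² = 3.61 kg.

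2. *One patient with true BMI change d below 1.* If the baseline falls evenly within the rounding interval, the rounded change is 1 with probability d and 0 with probability 1 − d. The root-mean-square (RMS) error is √(d(1 − d)).

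| True change at 1.70 m | d (kg/m²) | Recorded as exactly 0 | RMS error (kg/m²) |
|---|---|---|---|
| 0.5 kg | 0.5/2.89 = 0.17 | 83% | 0.38 |
| 1 kg | 1/2.89 = 0.35 | 65% | 0.48 |
| 2 kg | 2/2.89 = 0.69 | 31% | 0.46 |

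For a 1 kg change, the chance of recording 0 is 1 − 1/2.40 = 58% at 1.55 m and 1 − 1/3.61 = 72% at 1.90 m. Setting √(d(1 − d)) = d gives d = 0.5. The typical error is therefore larger than the true change only below 0.5 kg/m², which is 0.5 × 2.89 = 1.4 kg at 1.70 m.

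3. *Summary statistics for an arm* (200,000 simulated patients, 1.70 m; BMI change in kg/m², true → rounded).

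| Weight change, mean (SD) | Mean | SD | Median | SE of mean, n = 48 |
|---|---|---|---|---|
| 0 kg (1 kg) | 0.001 → 0.001 | 0.346 → 0.527 | 0.001 → 0 | 0.050 → 0.076 |
| 1 kg (1 kg) | 0.345 → 0.345 | 0.346 → 0.540 | 0.346 → 0 | 0.050 → 0.078 |
| 1 kg (2 kg) | 0.348 → 0.348 | 0.692 → 0.802 | 0.348 → 0 | 0.100 → 0.116 |
| 2 kg (1 kg) | 0.692 → 0.693 | 0.346 → 0.538 | 0.692 → 1 | 0.050 → 0.078 |
| 3 kg (2 kg) | 1.037 → 1.037 | 0.692 → 0.802 | 1.039 → 1 | 0.100 → 0.116 |

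Means are unaffected. SDs are inflated, and medians fall on whole numbers.

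4. *Agreement with the weight table.* At 1.70 m and BMI 28, weight is 28 × 2.89 = 80.9 kg, and a 1 kg change is 1/80.9 = 1.2%. For a patient whose baseline BMI is recorded as 28, the BMI table can show that change only as 0% or 1/28 = 3.6%.

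5. *Eligibility, only if the rounded value were used.* BMI from 17.5 to just under 40.5 would pass. At 1.70 m, 17.5 × 2.89 = 50.6 kg against 18 × 2.89 = 52.0 kg, and 40.5 × 2.89 = 117.0 kg against 40 × 2.89 = 115.6 kg. That is 1.4 kg at each end.

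6. *After the fix.* Unrounded BMI has no rounding error. Even if BMI were stored to one decimal, the error in a change would stay below 0.1 kg/m².

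**The case against.** The best defence is that no sentence says BMI is rounded before the change is taken. The change formula covers weight alone, and two other sections define BMI without rounding, so the rule could be meant for display. This stands in part, because the order is an inference. Display is the less likely meaning, however. SAP 4.2 already sets display precision for all summaries, and SAP 4.11.8 puts the rounding in the derivation, ahead of the change calculation. If unrounded values were intended, the text needs to say so.

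The second defence is that little is lost. This stands. Weight change is summarised in the same section without a rounding rule. With height fixed, it carries all the information in BMI change. No hypothesis test or stopping rule uses BMI.

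A reader might go further in four ways that the documents do not support.

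- *That rounding error exceeds the changes being summarised.* The documents give no expected weight change. The statement is true for individual changes below about 0.5 kg/m², but not for larger ones or for arm means.
- *That every change carries an added error with SD √(2/12) = 0.41 kg/m².* That figure treats the two rounding errors as independent. For a given patient the error is √(d(1 − d)), which is 0 when there is no change and 0.30 at d = 0.1. The 0.41 is about what results on average over a spread of changes.
- *That the eligibility limits are loosened.* Criterion 3 is written without rounding, SAP 4.11.8 does not govern enrolment, and the eligibility sentence in Protocol 8.1.4 concerns body weight. Loosening is possible only if a site applied the rounding rule to criterion 3.
- *That baseline BMI will differ between the demographic and safety tables.* SAP 4.6 is silent on rounding. It does not say that the eCRF value is unrounded, so a mismatch is not established.

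**Conclusion.** The point holds as a minor one. Followed on its natural reading, a stated derivation rule makes the summary of a named safety endpoint less precise and brings no benefit. The loss falls on the SD, median, quartiles, range and by-patient changes. Arm means stay practically unbiased, although at 48 patients per arm their standard error rises by roughly 16% to 56% in the assumed cases (0.100 to 0.116, and 0.050 to 0.078).

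These sizes rest on assumed heights, weight changes and baseline BMI, and on the change being taken from rounded values. The direction does not depend on the particular heights or weight changes chosen. No study conclusion is at risk, since the weight summary is available without a rounding rule. The eligibility question is a matter of unclear wording, with no evidence in the documents that any patient was admitted outside the limits.

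**What to change.** - Delete the whole-number rounding of BMI in SAP 4.11.8 and Protocol 8.1.4.
- In SAP 4.11.8, define BMI at each visit as weight at that visit over screening height squared, unrounded. Write out the absolute and relative change for BMI as is done for weight, using those unrounded values.
- Round for display only, under the precision rules of SAP 4.2.
- Reconcile Protocol 8.1.4 with inclusion criterion 3 by stating whether the rounded or the unrounded BMI is compared with the limits.

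The cost is a few lines of wording and a small change to the programming specification. Weight and height are already collected, so no new data are needed. Relative BMI change would then match relative weight change patient by patient, which also gives a simple programming check.

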4.12 Determination of Sample Size

CCI

CCI

4.13 Changes in the Conduct of the Study or Planned Analysis

Protocol amendments don't have statistical implication.

Results of upper endoscopy from investigator or endoscopy specialist will not be simply overridden by central reading. The records will be kept and described (LA grade and healing response) and the concordance with central reading will be investigated.

Descriptive table of the investigator or endoscopy specialist's results will be prepared, as well as a concordance table of the investigator or endoscopy specialist and central reading results.

6 APPENDICES

6.1 Schedule of Assessments

Table 1 Overall Schedule of Assessments

Visit	Visit 1 Screening	Visit 2	Visit 3	Visit 4	Visit 5	Tel Visit 6	Tel Visit 7	Tel Visit 8	Visit 9 End of Study / Early Termination
Assessment/Study day	Day -7 ¹⁴ to Day 0	Day 0	Day 7 ±2 days	Day 14 ±3 days	Day 28 -2/+5 days	Day 35 ±3 days	Day 42 ±3 days	Day 49 ±3 days	Day 56 ±3 days
Assessment/Study week		Randomization	Week 1	Week 2	Week 4	Week 5	Week 6	Week 7	Week 8
	Screening Period	Blinded Treatment Phase					Open-Label Phase		
Informed consent	X								
Demographics	X								
Inclusion/exclusion criteria	X	X							
Medical/surgical history ¹	X								
Weight, height ²	X				X				X
Complete physical examination	X				X				X
Drugs of abuse	X								X

Visit	Visit 1 Screening	Visit 2	Visit 3	Visit 4	Visit 5	Tel Visit 6	Tel Visit 7	Tel Visit 8	Visit 9 End of Study / Early Termination
Assessment/Study day	Day -7 ¹⁴ to Day 0	Day 0	Day 7 ±2 days	Day 14 ±3 days	Day 28 -2/+5 days	Day 35 ±3 days	Day 42 ±3 days	Day 49 ±3 days	Day 56 ±3 days
Assessment/Study week		Randomization	Week 1	Week 2	Week 4	Week 5	Week 6	Week 7	Week 8
	Screening Period		Blinded Treatment Phase				Open-Label Phase		
Viral serology testing ³	X								
Vital signs ⁴	X		X		X				X
12-lead ECG evaluation	X		X		X				X
Safety laboratory ⁵	X		X		X				X
H. pylori testing ⁶	X								
Pregnancy test ⁷	X				X				X
Randomization		X							
Patients provided with study drugs for blinded phase		X	X	X					

Visit	Visit 1 Screening	Visit 2	Visit 3	Visit 4	Visit 5	Tel Visit 6	Tel Visit 7	Tel Visit 8	Visit 9 End of Study / Early Termination
Assessment/Study day	Day -7 ¹⁴ to Day 0	Day 0	Day 7 ±2 days	Day 14 ±3 days	Day 28 -2/+5 days	Day 35 ±3 days	Day 42 ±3 days	Day 49 ±3 days	Day 56 ±3 days
Assessment/Study week		Randomization	Week 1	Week 2	Week 4	Week 5	Week 6	Week 7	Week 8
	Screening Period		Blinded Treatment Phase				Open-Label Phase		
Patients provided with Lansoprazole 30 mg for open-label phase					X				
PK blood sampling ⁸			X	X	X				
Upper endoscopy	X ¹⁵				X				
Symptom evaluation using QOLRAD Heartburn ⁹		X	X	X	X				X
Daily symptom diary (mRESQ-eD) completion by patient		X	X	X	X	X	X	X	X
Symptom diary provision/training/ review ¹⁰		X	X	X	X	X	X	X	X

Visit	Visit 1 Screening	Visit 2	Visit 3	Visit 4	Visit 5	Tel Visit 6	Tel Visit 7	Tel Visit 8	Visit 9 End of Study / Early Termination
Assessment/Study day	Day -7 ¹⁴ to Day 0	Day 0	Day 7 ±2 days	Day 14 ±3 days	Day 28 -2/+5 days	Day 35 ±3 days	Day 42 ±3 days	Day 49 ±3 days	Day 56 ±3 days
Assessment/Study week		Randomization	Week 1	Week 2	Week 4	Week 5	Week 6	Week 7	Week 8
	Screening Period		Blinded Treatment Phase				Open-Label Phase		
Symptom assessment by Investigator ¹¹	X	X	X	X	X	X	X	X	X
AE reporting ¹²	X	X	X	X	X	X	X	X	X
Prior/concomitant medications ¹³	X	X	X	X	X	X	X	X	X

Abbreviations: AE, adverse event; ECG, electrocardiogram; ICF, informed consent form; LA, Los Angeles; PK, pharmacokinetic.

1. Including smoking (current status), alcohol consumption, and intake of drug of abuse.
2. Height only at screening
3. Human immunodeficiency virus (HIV), hepatitis B surface antigen (HBsAg), hepatitis B core antigen (anti-HBcAg), antibody to hepatitis C virus (anti-HCV) testing at central and/or local laboratory. Patient should discontinue the study if result from central laboratory is positive.
4. Systolic and diastolic blood pressure (BP) [mmHg], heart rate [beats per minute], body temperature and respiratory rate [per minute].
5. Hematology, blood chemistry, coagulation (central laboratory), urinalysis (at site). Serum gastrin at screening and at Visit 5 (central laboratory).
6. *H. pylori* will be analyzed in central laboratory from serum and the result will not be needed for randomization.
7. Women of childbearing potential only. Serum pregnancy test at central laboratory at screening and urine pregnancy test at clinic/investigational site prior to the dose administration at Visit 5, and at End of Study / Early Termination.

8. PK measured in all patients just before the first and the second dose on the day of the visit. At all PK sampling occasions, the time since latest study drug administration must be noted in the case report form (CRF). Pharmacokinetic samples will be collected 12 hours after the previous study drug dose administration or as close to this timepoint as possible, however, still pre-dose.
9. QOLRAD assessment must be done pre-dose. QOLRAD will be completed by patients during site visits at Visit 2, 3, 4, 5 and 9.
10. Patients will be trained on how to complete the symptoms diary during Visit 2 and the actual diary will be provided at Visit 2.

4.5.4 Exploratory Efficacy Analyses	14
4.5.5 Subgroup Analyses.....	15
4.5.5.1 Subgroup analyses for the primary efficacy endpoint Healing	15
4.5.5.2 Subgroup analyses for two secondary efficacy endpoints	16
4.5.5.3 Subgroup analyses for Healing by local reading	16
4.5.5.6 Sensitivity Analyses	16
5. References	17

Abbreviations

Abbreviation	Term
AE	Adverse Event
AESI	Adverse Event of Special Interest
BMI	Body Mass Index
CSPCSP	Clinical Study Protocol
ECGECG	Electrocardiogram
eDiary	Electronic Diary
FAS	Full Analysis Set
FDAFDA	Food and Drug Administration
GERDGERD	Gastro-Esophageal Reflux Disease
H. Pylori	Helicobacter Pylori
ICF	Informed Consent Form
ICH	International Conference on Harmonization
IMP	Investigational Medicinal Product
LA grade	The grade of esophagitis according to the Los Angeles classification system
mFAS erosive	Modified Full Analysis Set erosive
mRESQ-eD	modified Reflux Symptom Questionnaire electronic Diary
PKPK	Pharmacokinetic
PKS	Pharmacokinetic Analysis Set
PRPR	Partial Response
PPI	Proton-pump inhibitor
PPS	Per-Protocol Analysis Set
SAE	Serious Adverse Event
SAP	Statistical Analysis Plan
SSSS	Safety Analysis Set
TEAE	Treatment Emergent Adverse Event
QDQD	Once daily (quaque die)
QOLRADQOLRAD	Quality of Life in Reflux and Dyspepsia

1. Introduction

Study CX842A2201 was subject to procedural changes after study start, in accordance with FDA advice. The changes rendered unforeseen consequences which were partly missed in the Statistical Analysis Plan (SAP) signed before unblinding the data of the study. The pre-specified SAP, "249403_SAP_20221013_v1.0.docx", will be referred to as the "original SAP".

The current document is SAP amendment complementary to the original SAP. In this document it is assumed that the original SAP is followed unless otherwise stated, but the text written in this SAP amendment overrides the original SAP.

Section 2 summarizes the study objectives and endpoints. Section 3 gives an overview of the procedural changes to the study, including timelines, problems that arose and solutions implemented. Section 4 (Analysis methods) defines all analysis sets and subgroups, lists all analyses that are to be done for each analysis set and subgroup. The hierarchy of different study results, as a consequence of the procedural changes, is based on whether the analysis was prespecified in the original SAP and/or in the clinical study protocol (CSP), "249403 02.01.02 Protocol 03 Sep 2020 English 1.0 Clean.pdf", or not prespecified. This hierarchy is explained in Section 4.3.3.

2. Study objectives and endpoints

This table is identical to that in the original SAP, except the Healing by local reading has been defined as an exploratory endpoint (bottom line).

Objectives	Endpoints
Primary	
The primary objective of the study is to support dose selection for X842, through assessment of healing of erosive esophagitis due to GERD after 4 weeks of treatment.	Healing of erosive esophagitis due to GERD based on endoscopic assessment after 4 weeks of double-blind treatment.
Secondary	
Evaluate the safety and tolerability of the four dose levels of X842 and lansoprazole, where lansoprazole will serve as the active comparator.	Physical examination, weight, BMI, vital signs, electrocardiogram (ECG) recordings, safety laboratory measurements (hematology/clinical chemistry/urinalysis), adverse event (AE), treatment emergent adverse event (TEAE), adverse event of special interest (AESI), serious adverse event (SAE) reporting, concomitant medication(s).

Objectives	Endpoints

Evaluate the reflux related symptom pattern during the initial 4 weeks treatment with four dose levels of X842 and with lansoprazole, and the symptom pattern during the subsequent additional 4 weeks (Weeks 5-8) open-label treatment with lansoprazole 30 mg QD.
	
 Percentage of heartburn-free 24-hour days during the Weeks 1-8 (Visits 2-9) based on eDiary (mRESQ-eD), including splits into day- and nighttime evaluations Percentage of 24-hour days with at most mild heartburn symptoms during the Weeks 1-8 (Visits 2-9) based on eDiary (mRESQ-eD), including splits into day- and nighttime evaluations Investigator assessment of symptom at Weeks 1-8 (Visits 2-9) Reflux related impact as measured by change from baseline in QOLRAD scores assessed after 1, 2, 4 and 8 weeks of treatment.
Exploratory	
CCI	

3. Background and timelines of unforeseen study events

This SAP amendment is written after the unblinding of study data, as motivated by some unforeseen events that occurred after the study start, and for which solutions were only partially captured in the original SAP. The sequence of events is summarized in

Abbreviations: CSP = Clinical Study Protocol, FDA = Food and Drug Administration, FAS = Full Analysis Set, FAS erosive = Full Analysis Set erosive, FAS erosive PR = Full Analysis Set erosive Partial Responders, mFAS erosive = modified Full Analysis Set erosive, SAP = Statistical Analysis Plan. # and *: References between panels describing the same issue. and below.

A change in study proceedings was committed after study start according to advice from FDA. It was agreed that instead of letting the assessments of LA grade of erosive esophagitis due to GERD rely on the judgement of the local investigator at the clinic at the time of endoscopy, images taken at the endoscopy were to be sent for a central review, and these central readings were to define the LA grade of patients in the study.

LA grades A, B, C and D represent increasing severity of erosiveness, and non-erosive patients are classified with LA grade 0 (zero). The LA grades define both the patients' level of disease at Baseline (grade A, B, C or D), and the primary efficacy endpoint healing of erosive esophagitis after 4 weeks of treatment (grade 0 corresponds to "healed", and grade A, B, C or D corresponds to "not healed").

[figure not shown]
Each patient was therefore included in the study based on local assessments, however, was later re-classified by central readings. This gave 2 immediate consequences, which are adhered to in this SAP amendment:

1. Non-erosive patients were included in the study and in the FAS (the analysis set intended for the primary analysis) in disagreement with the CSP. This was solved in the original SAP by the creation of 2 subsets of FAS, including **FAS erosive** and **FAS non-erosive**, and specifying that the primary endpoint would be performed in both (implying the FAS erosive analysis to be the primary analysis of the study.). In this SAP amendment, these 2 subsets were instead defined as 2 separate analysis sets, to make subgroup analyses within them easier to describe. It is further clarified explicitly that the primary objective of the study will be assessed in FAS erosive, and analyses on the FAS non-erosive are seen as exploratory, as healing in non-erosive patients is not interpretable. This SAP amendment also clarifies to present demography, baseline characteristics, secondary, sensitivity and pharmacokinetic (PK) results for the FAS erosive, which were missed in the original SAP.
2. LA grade A/B patients without a history of PR to PPI were included in the study in disagreement with the CSP. According to the CSP, LA grade A/B patients were only to be included if they had at least partial symptom response but endoscopically still unhealed after 8 weeks' history of standard treatment healing course with PPI. For LA grade C/D patients, the study has no such additional inclusion criterion. Some patients entered the study classified as LA grade C/D patients according to their local reading, and were re-classified as LA grade A/B patients in the central reading. It was erratically believed that for these patients, information about prior response to PPI was never collected. For this reason, the original SAP was hastily adjusted so that instead of assessing LA grade A/B patients with prior PR to PPI and LA grade C/D patients, assessments would be done on LA grade A/B patients and LA grade C/D patients. After data unlock it was discovered that the prior PR to PPI information had in fact been collected for all patients, so it is hence possible to identify the patients which reflect the primary objective of the CSP. In this SAP amendment, the **FAS erosive PR** has been defined to capture this population.

During the study analysis stage, before this SAP amendment was written, a third issue appeared:

3. According to the original SAP, the primary endpoint healing should be imputed as "no" in patients for whom the 4-week endoscopy was never done. This was forgotten. Instead, the patients with no evaluation of the primary endpoint were dropped from analysis, so that healing results based on the subset of FAS erosive patients, who were evaluable at 4 weeks, were communicated officially as primary results of the study. To enable proper reference to this analysis in follow-up communication, the corresponding analysis set **mFAS erosive** was defined in this SAP amendment.

Figure 1.3-2. Flow chart to summarize the background reasons and timelines for decisions and changes regarding the analysis of the study data

Abbreviations: **CSP** = Clinical Study Protocol, **FDA** = Food and Drug Administration, **FAS** = Full Analysis Set, **FAS erosive** = Full Analysis Set erosive, **FAS erosive PR** = Full Analysis Set erosive Partial Responders, **mFAS erosive** = modified Full Analysis Set erosive, **SAP** = Statistical Analysis Plan. # and *: References between panels describing the same issue.

All study analysis sets are defined in Section 4.3. The issues and their solutions, as well as timelines, renders a hierarchy of how different results from the different analysis sets are interpreted. This is specified in Section 4.3.3.

4. Analysis Methods

